3.3.3. End-points

Primary End-point:

1. Progression Free Survival (PFS) for patients with ad/mRCC receiving SU.

PFS is defined as: the time from when the patient receives the first dose of SU to the time of progression or death due to any cause, which occurs first.

2. Time to Treatment Failure (TTF) for SU 1st line.

TTF is defined as: from when the patient receives the first dose of SU to the time of SU discontinuation (date completed by the physician).

Secondary End-point:

1. Objective Response Rate (OOR) for adv/mRCC patients receiving SU as 1st line treatment.

ORR is defined as the percentage of patients with confirmed CR or confirmed PR according to RECIST criteria v1.1.

2. Description of SU real life usage of doses across all centers, including description of treatment schedules (dose change, dose schedule, average dose received during the period treatment).

3. Combined PFS for patients with ad/mRCC receiving the 2nd line sequence SU- different treatment.

Combined PFS is defined as: the time from when the patients receives the first dose of SU as first line, until progression or death due to any cause while on the 2nd line treatment, whichever occurs first during the 2nd line sequence treatment.

4. Combined TTF for the SU-2nd line sequence.

Combined TTF is defined: as the time from when the patient receives the first dose with SU as first line, to the time of 2nd line sequence discontinuation (date completed by the physician).

5. OS for adv/mRCC patients receiving SU as first line followed by 2nd line as measured from date of first SU dose to the date of death of any cause. The OS median and the overall survival at month 24 (24 months OS) will be measured.
6. If possible, efficacy parameters (PFS, OS) for the combined 1st line SU- 2nd line sequences according to the second line post SU (other than SU-AXI):
 - SU in 1st line-Axitinib TKI in 2nd line.
 - SU in 1st line- other TKI in 2nd line (sorafenib, pazopanib).
 - SU in 1st line/mTOR in 2nd line (temsirolimus, everolimus).
7. Safety description with AE listing in patients receiving SU: frequencies of patients experiencing at least one AE will be displayed by body system.
8. QoL using the questionnaire Functional Assessment of Cancer Therapy-Kidney Symptom Index 19 (FKSI-19).

CCI

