8.7. Sample Size

Due to the non-existence of a sample size calculation/justification for estimating the median progression free survival in phase IV trials and the exploratory/observatory nature of this study, we opt not to base the sample size on the main objective. However, we will use the secondary objective of estimation of the ORR for adv/mRCC patients receiving SU in the 1st line as the basis of the sample size. With 140 patients we will be able to assess the ORR to within a margin of error of at most $\pm 8\%$ using 95% confidence intervals. This is based on the assumption that the ORR will be less than 37% as per the literature.^{12,25} This sample size is also within the range of sample sizes of other studies investigating SU for first line and where PFS and TTF were estimated.²⁵

The 140 patients will be enrolled at 14 sites in the Middle Eastern & African countries; namely UAE, Qatar, RSA, Egypt, Algeria, Tunisia and Morocco. Each site is expected to enroll an average of 10 patients. This will ensure diverse and possibly representative sample of the Middle East and North Africa region.

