5.5. Covariates

- In case of multivariate analyses, baseline characteristics will possibly be used as covariates.
- The final covariates will be selected according to the selection strategy of variables defined in the part 7.6.
- Possible, but not exclusive, baseline covariates related to SU initiation will be limited because of a retrospective part of the data collection, with:
 - Age and sex;
 - ECOG (0, 1, 2, 3, 4), Karnofsky performance status
 - MSKCC risk factors (Favorable, Intermediate, Poor)

- Medical history of hypertension (Yes, No)
- Delay from diagnosis (< 1 year from diagnosis to first metastasis detection/ \geq 1 year)
- Nephrectomy (Yes, No)
- Number of metastatic sites
- The covariates identified previously will be also explored and act as baseline for second line treatment initiation. In this case, other covariates will be:
 - The response to SU treatment in 1st line;
 - Duration of SU treatment, PFS;
 - Previous treatments for primary tumor (surgery, radiotherapy, other);
 - Additional anti-tumor treatments;

6. Handling missing values

- The majority of data will be collected with a website (except for FKSI-19 questionnaires).
- In this website, the input of certain data will be obligatory, limiting the number of missing values, particularly for endpoints.
- Regarding the descriptive analyses of each variable, it will be based on the available data (“observed-case analysis”), considering missing data as non-informative.
- The number of missing data will be documented for each analysis.
- The analysis of the primary endpoint is a survival analysis which is known to efficiently handle missing data: All patients are included in the analysis and missing data are called right-censored data.
- In case of absence of 20% data and over, for a main parameter such as ORR rate, the Hot-deck imputation method could be used. With this method, the missing value is replaced by the observed value of a patient with similar characteristics $X_1, X_2 \dots X_k$. If it does not exist such similar patient, the missing value will be amputated
- A sensitivity analysis will be conducted by the imputation of extreme values. In the one hand, analysis in the most unfavorable situation (i.e. missing data considered as failure) and in the other hand, analysis in the most favorable situation, i.e. missing data considered as success (e.g. for ORR, success is to be responder).

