7.1. Descriptive methods

- Descriptive analysis of qualitative and ordinal variables will comprise the count and the frequency of each category.

- Descriptive analysis of quantitative variables will be presented by the mean and standard deviation (SD) for the data that follows a Gaussian distribution and the median and range otherwise.
- The 95% confidence intervals will be presented for main endpoints. The ‘exact’ Clopper-Pearson confidence interval will be provided to assess 2-sided 95% confidence interval for main binomial proportions (e.g. ORR rate).
- The number of missing values will be reported in the results table for each variable.

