8.1.2. Objective response rate

- **Role:**
- To assess the Objective Response Rate (ORR) for adv/mRCC patients receiving 2nd line post SU”
- **Population:**
Study population “SU – other sequence” patients
- **Endpoints:**
- Clinical Benefit Rate (CBR)
- Objective Response Rate (ORR)
- **Statistical methods:**
Descriptive analyses
- **Method for handling missing values:**
Hot-deck imputation method and imputation by extreme values

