Appendix 3: List of covariate and outcomes in the study

Variable	Role	Operational definition
Age	Covariate	Defined as the date of birth of the participant
Gender	Covariate	Defined as the male or female sex
Ethnicity	Covariate	Defined as race of Middle Eastern, Indian, Caucasian or African descendant
ECOG	Covariate	The ECOG Scale of Performance Status describes a patient's level of functioning in terms of their ability to care for themselves, daily activity, and physical ability (walking, working, etc.)
Number of metastatic sites	Covariate	Total number of site where metastasis is detected
Nephrectomy	Covariate	Surgical removal of the kidney
MSKCC risk	Covariate	The MSKCC risk system stratifies patients with mRCC into poor-, intermediate- and favorable-risk categories based on the number of adverse clinical and laboratory parameters present
Hypertension	Covariate	Presence of high systolic blood pressure >13mmHg
Previous medical treatment	Covariate	Presence of medical treatment related to the disease prior to SU initiation
PFS	Outcome	The PFS will be defined as the time from when the patient receives the first dose of SU to the time of progression or death due to any cause, whichever occurs first
OS	Outcome	OS defined as the time from date of first SU dose to the date of death of any cause.
ORR	Outcome	The objective response rate is the percentage of patients with a complete response (CR) or a partial response (PR) according to RECIST 1.1 criteria as best response, over the SU treatment period.
TTF	Outcome	TTF is defined as the time from when the patient receives the first dose of treatment to the date of SU discontinuation
Combined PFS	Outcome	The time from when the patients receives the first dose of SU as first line, until progression or death due to any cause while on the 2nd line treatment, whichever occurs first during the 2nd line sequence treatment.
Combined TTF	Outcome	The time from when the patient receives the first dose with SU as first line, to the time of 2nd line sequence discontinuation

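### The main ORR analysis has no non-responder rule for patients never assessed for response, and its population may leave early failures out

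*SAP*

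**What the plan says.** **Definition.** Protocol 3.3.3 states: "ORR is defined as the percentage of patients with confirmed CR or confirmed PR according to RECIST criteria v1.1", for patients receiving SU as first line. SAP Appendix 3 states: "The objective response rate is the percentage of patients with a complete response (CR) or a partial response (PR) according to RECIST 1.1 criteria", taken as best response over the SU treatment period, without mentioning confirmation. Neither says how a patient with no assessment is counted.

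**Missing data.** SAP section 6 bases descriptive analyses on available data, "considering missing data as non-informative". It then says: "In case of absence of 20% data and over, for a main parameter such as ORR rate, the Hot-deck imputation method could be used". The donor is a patient with similar characteristics. If there is none, the value is to be amputated, a word whose meaning here is unclear. A sensitivity analysis with missing as failure, then as success, will be conducted, with ORR as its example. Section 8.1.2 classes ORR as descriptive and lists, for missing values, "Hot-deck imputation method and imputation by extreme values".

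**Population.** SAP 8.1.2 gives the aim as ORR in patients receiving second line after SU, and names the SU–other sequence patients. SAP 2.3 and Protocol 3.3.2 give the objective as ORR under first-line SU. The efficacy population in SAP 4.1 requires at least 6 months of follow-up.

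**Timing and recording.** Protocol 8.2 expects tumour assessment about every 3 months, with a 6-week window for visits. Protocol 8.5 leaves the eCRF section blank when a parameter is not collected.

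**The concern.** A patient who dies before any post-baseline scan has a known result for this endpoint: no confirmed CR or PR. The same holds, under the SAP's definition over the SU period, for a patient who stops SU before being scanned. Such blanks are informative, so treating them as non-informative is hard to defend. Observed-case analysis removes these patients from the denominator. Hot-deck may give them the response of someone who was scanned.

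ORR is secondary, but it is the endpoint on which Protocol 8.7 sizes the study. It is also likely to be compared with the published rates used there, and a rate among patients who reached a scan is not comparable with a rate among all patients treated.

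**Working it through.** **1. The plan's own figure.** Protocol 8.7 says: "With 140 patients we will be able to assess the ORR to within a margin of error of at most" ±8%, and adds: "This is based on the assumption that the ORR will be less than 37% as per the literature". With p = 0.37 and the normal approximation:

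- margin = 1.96 × √(0.37 × 0.63 / 140) = 0.0800
- N for 8 points = 1.96² × 0.37 × 0.63 / 0.08² = 139.9, rounded up to 140

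The figure reproduces. SAP 7.1 uses the Clopper-Pearson method "to assess 2-sided 95% confidence interval for main binomial proportions". At 52/140 that gives 29.1% to 45.7%, a half-width of 8.3 points. The calculation takes all 140 patients as the denominator.

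**2. Observed-case ORR.** Let x be the responders, N the treated patients and m the share unassessed.

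- all treated, unassessed counted as non-responders: x/N
- observed-case: x/(N(1-m))
- ratio: 1/(1-m)

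The documents give no value for m, so the range below is an assumption. I use x = 41, because 41/112 = 36.6% is close to the planning value of 37% when 20% are unassessed. Then 41/140 = 29.3%.

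| Unassessed | m | Observed-case ORR | Gap to 29.3% (from unrounded values) |
|---|---|---|---|
| 7 | 5% | 41/133 = 30.8% | 1.5 points |
| 14 | 10% | 41/126 = 32.5% | 3.3 points |
| 21 | 15% | 41/119 = 34.5% | 5.2 points |
| 27 | 19% | 41/113 = 36.3% | 7.0 points |
| 28 | 20% | 41/112 = 36.6% | 7.3 points |

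The row with 27 unassessed is still below the hot-deck trigger. The choice of 41 does not drive the result: with 42 responders and 27 unassessed, 42/113 = 37.2% against 42/140 = 30.0%, a gap of 7.2 points.

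**3. Hot-deck.** With 28 unassessed and an expected donor response rate d, the expected ORR is (41 + 28d)/140.

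- d = 36.6%, donors average: 36.6%
- d = 20%, poorer-prognosis donors (illustrative): 46.6/140 = 33.3%
- d = 0: 29.3%

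Since d cannot be negative, hot-deck can only raise ORR, or leave it unchanged, relative to counting these patients as non-responders.

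**4. The sensitivity bounds.** With 28 unassessed, missing as failure gives 41/140 = 29.3% and missing as success gives 69/140 = 49.3%. A range of 20 points does not tell the reader which value is the estimate.

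**5. Population.** If the 6-month condition is applied to ORR, early deaths leave the denominator before any missing-data rule acts. The missing-as-failure analysis would not restore them. The second-line population can also exclude patients who die or fail before a second treatment. It may exclude patients still responding to SU too, so the direction of its net effect cannot be read from the documents.

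**The case against.** **The definition may already settle it.** Read literally, a percentage of patients with CR or PR keeps every treated patient in the denominator. No readable passage says that an early death is coded as missing for ORR; a reader might infer this from the blank-field rule and section 6, but it remains an inference. It is a reasonable one, because a separate missing-as-failure analysis would be redundant if the main analysis already counted these patients as failures.

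**Part of the SAP cannot be read.** The efficacy-endpoint text that would precede section 5.4 is not legible in the public copy, and a rule for non-evaluable patients may be there. This caveat stands. Even so, such a rule would sit uneasily with sections 6 and 8.1.2, which would still need reconciling.

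**The conservative analysis is the committed one.** Hot-deck is optional and starts at 20% missing, while the extreme-value analysis will be done. Section 8.1.2 does not name observed-case for ORR, whereas section 8.2 does for safety. That is fair, but below 20% the general rule in section 6 is then the only main-analysis rule visible for ORR.

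**Not every early failure escapes.** Disease status is updated at each visit, and progression recorded as PD is an observed non-response. A reader might infer that no early failure can lower ORR; the documents do not support that. The point concerns only patients never assessed.

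**Blanks may be few or administrative.** Section 6 makes certain entries obligatory, particularly for endpoints, and in routine care a scan may simply not be done. Both are possible. Obligatory entry cannot supply a response for a patient who was never scanned.

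**Weight.** ORR is secondary and descriptive in a study that Protocol 8.11 calls hypothesis-generating, and missing counts will be reported. This limits the consequence but does not settle the rule.

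**Conclusion.** The readable SAP lacks a non-responder rule for unassessed patients in its main ORR estimate. Its visible handling, observed-case or optional hot-deck, can overstate ORR relative to a rate among all SU-treated patients. For observed-case the factor is 1/(1-m). Under the assumption of 10% to 19% unassessed and 41 responders among 140, that is 3.3 to 7.0 points, the upper end close to the whole planned margin of 8.

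This rests on three assumptions: that unassessed patients are left blank and treated as missing, that few of them were true responders, and that m lies in the range shown. A reader might conclude that an inflated ORR is established. The documents do not support that, because they give no missing rate and the endpoint text is incomplete in the public copy. What is established is that the main rule is unstated, and that the ORR population in SAP 8.1.2 conflicts with the first-line objective in both documents. The change should be made before analysis.

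**What to change.** In SAP sections 6 and 8.1.2:

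- Define the main ORR population as all patients who received SU as first line, without the 6-month follow-up condition of section 4.1 and without the second-line condition of section 8.1.2. If ORR in second-line patients is also wanted, list it as a separate analysis.
- Count as a non-responder any patient with no qualifying response, including those never assessed because of death, clinical worsening, stopping SU or any other reason. State whether a qualifying response must be confirmed, since Protocol 3.3.3 and SAP Appendix 3 differ.
- Remove hot-deck imputation for ORR.
- Report the evaluable-patient ORR as secondary, with the number of unassessed patients and the reason for each.

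The cost is SAP wording and recording of a reason for each missing assessment; the missing-as-failure calculation is already planned. The headline ORR will be somewhat lower, and a true responder whose scan is missing for administrative reasons will count as a failure. The secondary analysis and the listed reasons let the reader judge how much that matters.

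### If single hot-deck values are counted in the Clopper-Pearson denominator for ORR, the nominal 95% interval covers only about 91% at 20% missing and 84% at 40%

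*SAP*

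**What the plan says.** SAP section 6 (Handling missing values) starts from observed cases for descriptive analyses, "considering missing data as non-informative". It then opens a second route: "In case of absence of 20% data and over, for a main parameter such as ORR rate, the Hot-deck imputation method could be used". The mechanism is single imputation, because "the missing value is replaced by the observed value of a patient with similar characteristics". For a patient without a match the text reads "If it does not exist such similar patient, the missing value will be amputated", which could mean dropped or imputed in some other way. The section also plans a sensitivity analysis that sets all missing responses to failure and then all to success, and it asks for the number missing in each analysis.

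SAP section 8.1.2 gives the missing-data method for ORR as "Hot-deck imputation method and imputation by extreme values", without repeating the 20% condition. SAP section 7.1 says that a "Clopper-Pearson confidence interval will be provided to assess 2-sided 95% confidence interval for main binomial proportions", with ORR as its example, and Protocol section 8.9 plans the same interval. No readable text says which denominator applies after imputation. None provides multiple imputation, a variance correction or a reduced n.

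Protocol section 8.7 sizes the study on ORR: "With 140 patients we will be able to assess the ORR to within a margin of error of at most" 8 points. "This is based on the assumption that the ORR will be less than 37% as per the literature".

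**The concern.** A Clopper-Pearson interval assumes that n independent outcomes were observed. A copied donor value adds no information, yet it adds one to n if the interval is run on the completed data. The interval then ignores two things: fewer than n responses were seen, and the choice of donor adds noise of its own.

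ORR is a secondary endpoint, but it sized the study, and the width of its interval is the only precision that the protocol states. Missing responses are plausible. Protocol section 8.5 leaves uncollected items blank, and section 8.2 leaves tumor assessment to local practice at roughly three-month intervals. An interval that stays close to the design target whatever is missing would suggest that the target had nearly been met when it had not.

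**Working it through.** **Inputs.** From the documents: 140 patients and ORR 37% (Protocol 8.7), a two-sided 95% Clopper-Pearson interval (SAP 7.1), and a trigger at 20% missing with one donor per missing value (SAP 6). Assumed: 20%, 30% or 40% missing, completely at random; a random observed donor drawn with replacement; and the interval computed on all 140.

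**The plan's own figure.** n = 1.96² × 0.37 × 0.63 / 0.08² = 139.9, so 140, with half-width 1.96 × √(0.37 × 0.63 / 140) = 8.00 points. The stated figure reproduces under the normal approximation. With the planned Clopper-Pearson method, 52/140 gives 29.1% to 45.7%, a half-width of 8.29. Averaged over samples at a true ORR of 37%, the half-width is 8.25.

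**Variance.** Let r be the number observed, m = n − r the number imputed, and f = m/n. The completed-data proportion has variance of about p(1−p)[1/r + m/n²], while the interval uses about p(1−p)/n. The ratio is n/r + m/n = 1/(1−f) + f:

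- f = 0.20: 1.250 + 0.20 = 1.450, so the standard error is 1.20 times the one used.
- f = 0.30: 1.429 + 0.30 = 1.729, so 1.31 times.
- f = 0.40: 1.667 + 0.40 = 2.067, so 1.44 times.

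The ratio depends on the missing share and not on n.

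**Width and coverage.** Results are from 200,000 simulated studies per row at ORR 37%, with half-widths in points. The needed half-width is 1.96 times the true standard error of the hot-deck estimate.

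| Missing | Observed r | Half-width, completed 140 | Half-width needed | Half-width, observed cases | Coverage, completed 140 | Coverage, observed cases |
|---|---|---|---|---|---|---|
| 20% | 112 | 8.24 | 9.62 | 9.24 | 90.7% | 95.9% |
| 30% | 98 | 8.23 | 10.51 | 9.89 | 87.5% | 96.5% |
| 40% | 84 | 8.22 | 11.48 | 10.69 | 83.8% | 95.8% |

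Hand check at 20%: the true standard error is 9.62 / 1.96 = 4.91 points, 8.24 / 4.91 = 1.68, and 2Φ(1.68) − 1 = 0.907.

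**The switch.** With 27 of 140 missing (19%), the observed-case interval on 113 patients has half-width 9.20. With 28 missing (20%) and hot-deck, it is 8.24. Losing one more response improves reported precision by 0.96 points.

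**Robustness.** Coverage at 20%, 30% and 40% missing:

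- True ORR 25%: 91.2%, 88.4%, 84.8%.
- Donors drawn without replacement: 91.1%, 89.0%, 86.6%.
- Matching within three strata with ORR of 50%, 37% and 20%: 91.3%, 88.4%, 84.9%.

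**The planned bounds.** With 41 responders among 112 observed, the worst case is 41/140 = 29.3% (21.9% to 37.6%) and the best case is 69/140 = 49.3% (40.7% to 57.9%).

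**The case against.** The strongest reply is that this is a fallback and not the main plan. Section 6 starts from observed cases, and hot-deck needs both 20% missing and a decision to use it. The documents give no likelihood for either. Section 8.1.2 drops the condition but can be read as pointing back to section 6. This stands as a limit on the claim: a reader might infer that the SAP always imputes missing responses, and section 6 does not say so. It does not remove the flaw. If the option is taken, no adjustment is provided, and leaving the decision open allows it to be made after the data are seen.

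Second, the completed-data denominator is inferred. Part of the SAP between sections 4.2 and 5.4 is redacted or unreadable in the public text and may hold a denominator rule. The unclear no-donor sentence may also mean that some patients are dropped. Both points stand, which is why the conclusion is conditional on imputed values entering n.

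Third, the worst/best-case analysis and the missing counts are already planned, and the bounds at 20% missing span 20 points, far more than the error in the interval. They do show the uncertainty. They still leave an interval labelled 95% that does not have that coverage.

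Fourth, 140 is not the SAP's ORR denominator. Section 4.1 limits the efficacy population to patients with at least 6 months of follow-up, and section 8.1.2 names a second-line sequence population. This stands for the half-widths, which are illustrative. The standard-error ratio does not depend on n.

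**Conclusion.** The concern holds in conditional form. If hot-deck is used and its values count in the Clopper-Pearson n, the ORR interval is too narrow. Nominal 95% coverage is about 91%, 88% and 84% at 20%, 30% and 40% imputed, against about 96% for observed cases.

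A reader might infer that the interval shrinks steadily as more data go missing. It does not. At ORR 37% the half-width stays near 8.2 points while the width needed grows, and the only drop is the single step of about 1 point at the 20% switch.

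The figures rest on assumed missing shares and on responses missing completely at random. The good coverage of the observed-case interval needs the same assumption. If missingness depends on outcome, both estimates can be biased, and the worst/best-case bounds are what speak to that.

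The consequence is limited: ORR is secondary and Protocol section 8.11 describes the study as hypothesis-generating. Even so, the interval should be corrected, because ORR precision is the stated basis of the sample size and the change is cheap.

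**What to change.** In SAP section 6, delete the single hot-deck option, the 20% switch and the unclear no-donor sentence. Delete the hot-deck entry in section 8.1.2. Then choose one of two routes in advance:

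- Report the Clopper-Pearson interval on the observed denominator, already the section 6 default for descriptive analyses, with the planned worst/best-case bounds beside it.
- Use multiple imputation with a prespecified covariate list and at least 20 sets, combined by Rubin's rules on the logit scale.

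In either case, state in section 7.1 that imputed values never enter the Clopper-Pearson n.

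The first route costs SAP wording only, and the second adds a small programming task. Neither needs new data. In the illustration, the observed-case interval is wider on each side by 9.24 − 8.24 = 1.0 point at 20% missing and by 10.69 − 8.22 = 2.5 points at 40%.
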